## 2.4 Determination of sample size

There is no formal sample size calculation for this study. The sample size is determined by the number of subjects eligible for PA0009 and rolling over from PA0008. Up to 200 subjects from PA0008 could be enrolled into this study.

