- The  $m$  datasets are summarized.
- The results of the  $m$  summaries are combined into a single result.

The MI method will be applied as follows:

### Step 1

- Create a data set, sorted by treatment group at completion of PA0008, of subjects with observed values and missing values needing imputation. Missing values will be separated into non-monotone (ie, intermittent missing values between completed assessments) and monotone (ie, missing values after the subject dropped out). The procedure will sequentially estimate an imputation model for the efficacy variable at each post-PA0008 Baseline visit where efficacy variables are collected, with PA0008 Baseline, geographic region, and past TNF inhibitor exposure (as collected on the eCRF in PA0008 for past anti-TNF exposure) as covariates, separately for each treatment group at the completion of PA0008.
- Intermittent missing data will be imputed by draws from the imputation model using the Markov-Chain Monte Carlo (MCMC) method with multiple chains and monotone imputing. A total number of imputations will be 100. The seed used for these imputations will be 2017.

Note: All MI procedures described in this SAP will use the same seed.

- The post-PA0008 Baseline values will be specified in chronological order in the imputation model so that the SAS® PROC MI imputes variables from left to right. If a PA0008 Baseline raw value is missing, the study participant will be excluded. The imputation model based on the MCMC method will only allow multivariate normal variables as predictors. Therefore, past TNF inhibitor exposure and geographic region will be re-coded as indicator variables. For past TNF exposure, this will be 0 for no past exposure and 1 for past TNF exposure. Similarly, for region, this will be 1 for subjects from Europe and 0 for all other subjects. The order for the covariates in the model will be as follows: region indicator variable (Europe = 1, North America = 0), past TNF exposure (Yes = 1, No = 0), Baseline value, and visit variables.
- Once the intermittent missing data are imputed, the monotone missing data will be imputed including covariates as defined above, based on the datasets created by the intermittent missing data MI. Since this dataset already has 100 imputed values at each visit, only 1 imputation will be performed.

## Step 2

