### Step 3 (CRP only)

The CRP data will be presented using the geometric mean, 95% confidence interval (CI) for the geometric mean, median, Q1, Q3, minimum and maximum. The change from Baseline will be expressed as the ratio to Baseline in the summaries. The following approach will be applied:

- Following the MI procedure the ratio to Baseline will be calculated for any of the imputed values
- The natural logarithm of the absolute values and of the ratios to Baseline will be calculated
- The logged values will be summarized by treatment, visit and imputation
- The datasets will be combined using PROC MIANALYZE in order to get the mean and 95% CI estimates from the absolute values and ratios to Baseline (based on logged data) across imputations
- The estimates of the mean and 95% CI will be back-transformed to obtain the geometric mean and 95% CI on the original scale
- For the median, Q1, Q3, minimum and maximum the procedure outlined above for the other endpoints will be followed

As a sensitivity analysis, certain efficacy variables will be summarized based on observed data (see [Section 8](#)).

As a further sensitivity analysis for ACR and PASI responses, the response variables will be derived following MI of the individual components for ACR or following MI of the overall PASI score. The ACR and PASI responses will then be derived for each subject and each imputation (where each imputation is performed across all individual components for ACR) and the number and percentage of subjects with each ACR and PASI response in each imputation will be

calculated. The mean value (across imputations) for the percentage of subjects with each ACR or PASI response will be reported.

A similar approach will be followed for the calculation and summary of the number and percentage of subjects with normal HADS scores (defined as having HADS-D and HADS-A <8 at the same visit) based on the HADS-D and HADS-A values after MI.

Primary and sensitivity analyses are summarized in Table 4–2. All summaries presenting data following MI will include only visits from PA0009 EV onwards (although the MI procedure will incorporate data from both PA0008 and PA0009).

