### 5.1.1 Impact of COVID-19

A listing of all visits affected by COVID-19 will be presented based on the Enrolled Set including the visit, date of visit, relationship to COVID-19, impact category and a narrative (short description) of the event. This data will be summarized by treatment group at completion of PA0008, and overall for the ES for the following:

- Impact of COVID-19 for any reason
- Impact of COVID-19 for any reason by country

In addition, in order to assess the potential impact of COVID-19 on the collection and reporting of efficacy data a separate listing and summary will be presented to display missing data and data collected via an alternative modality (eg, phone, video call). For the purpose of these displays, missing data will be presented only for visits affected by COVID-19 (as reported on the dedicated eCRF page) ie, missing data at other visits and for other reasons will not be included.

The following efficacy assessments may be collected remotely:

- HADS
- HAQ-DI
- SF-36
- PGADA
- PtAAP
- PsAID-9

For visits conducted remotely (as reported on the dedicated eCRF page), it is not possible to assess MASES, PhGADA, BSA, PASI, LDI, TJC or SJC, and therefore these assessments will be missing at the specified visit. In addition, for any missed visit or a visit conducted remotely, the CRP assessment will also be missing. Such assessments will be considered to be missing as a result of COVID-19. For these visits, it will therefore not be possible to assess DAS28(CRP) and may not be possible to classify the subject as an ACR responder or nonresponder.

A listing will be presented showing each impacted visit based on the FAS. This will include the planned visit, the visit date, and details of the assessments conducted remotely and/or those missing as a result of COVID-19.

These data will be presented in a summary table by treatment group at completion of PA0008 and overall for the FAS.

For both the listing and the summary table, only visits at which efficacy assessments are scheduled will be included.

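### The ACR multiple-imputation sensitivity analysis imputes each component from its own history, so residual same-visit correlation between components is not modelled and the reported rate may shift by roughly 0.5 to 4 points

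*SAP*

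**What the plan says.** SAP 4.2.1 lists TJC, SJC, PGADA, PhGADA, PtAAP, HAQ-DI and CRP as separate MI endpoints. Step 1 describes one variable at a time: "The procedure will sequentially estimate an imputation model for the efficacy variable at each post-PA0008 Baseline visit where efficacy variables are collected", fitted "separately for each treatment group at the completion of PA0008". The model terms, in order, are "region indicator variable (Europe = 1, North America = 0), past TNF exposure (Yes = 1, No = 0), Baseline value, and visit variables". SAP 4.1 names only region and past TNF inhibitor exposure as covariates for all MI models. There are 100 imputations and one seed, 2017: "Note: All MI procedures described in this SAP will use the same seed".

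Later in 4.2.1 (in the text printed under Step 3 for CRP) the ACR sensitivity analysis is defined: "the response variables will be derived following MI of the individual components for ACR". Response is derived per subject and per imputation, and the percentages are averaged over imputations. SAP 8 describes it differently: response is re-derived from the component scores averaged over imputations.

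SAP 8.1.8 requires improvement in TJC, SJC and at least 3 of the other 5 measures. SAP 5.1.1 says that at remote visits "it is not possible to assess MASES, PhGADA, BSA, PASI, LDI, TJC or SJC". CRP is missing too, while PGADA, PtAAP and HAQ-DI may still be collected. SAP 8.5 places the start of the pandemic after every subject had completed Week 48. Table 4-2 makes NRI the primary method for ACR, with MI and OC secondary. On size, SAP 2.4 states "There is no formal sample size calculation for this study" and "Up to 200 subjects from PA0008 could be enrolled into this study".

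**The concern.** ACR response is a joint event on seven measurements of one subject at one visit, so its rate depends on how the seven move together as well as on each one's distribution. A set of univariate models can reproduce every component well and still give the wrong frequency of joint improvement.

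Remote visits add a loss of information. A subject's pain, global and function scores for that day are on file, yet the joint counts for the same day are imputed without them. SAP 4.2.1 assumes data are missing at random, and that assumption is weaker when observed, related scores are left out of the model.

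At stake is how well the MI table serves as a missing-at-random comparison with NRI.

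**Working it through.** **1. Inputs.** From the SAP: the model terms, composite rule, number of imputations, seed and maximum of 200 subjects, as above. The documents give no component correlation, dropout rate or expected response rate, and no stated figure to reproduce. Those values below are assumptions, shown over a range.

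**2. Why correlation matters.** Let each component meet its threshold with probability p. If the seven are independent,

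P(ACR) = p² × P(Binomial(5, p) ≥ 3).

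For p = 0.6 this is 0.36 × 0.683 = 0.246. With same-visit correlation ρ, by Monte Carlo:

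| p | ρ = 0 | ρ = 0.4 | ρ = 0.6 | ρ near 1 |
|---|---|---|---|---|
| 0.6 | 24.5% | 35.5% | 41.0% | 59.1% |
| 0.7 | 41.1% | 48.8% | 53.1% | 69.2% |
| 0.8 | 60.2% | 63.8% | 66.8% | 79.3% |

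This overstates the loss under the SAP, because each component's own history carries part of the correlation. Only the residual part is lost.

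**3. Imputation simulation.** Setting: 100 subjects, 6 visits, 7 normal components, subject effect 0.4, autoregression 0.5, monotone dropout of all components together, 20 imputations, 60 replicates. Ranges: residual same-visit correlation 0.3-0.7, 10-30% missing, p of 0.6 or 0.8. Three models were compared with the full-data rate at the last visit:

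| Model | Shift in overall rate (points) | Shift among subjects with missing data (points) |
|---|---|---|
| Own history, independent draws | -0.5 to -4.0 | -2.9 to -12.8 |
| Own history, identical random stream for every component | +0.1 to +3.2 | +1.0 to +13.4 |
| Own history plus components already imputed at that visit | -0.9 to +0.2 | -3.6 to +1.1 |

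Example with correlation 0.5, 20% missing and p = 0.6: full data 38.7%; own history with independent draws 37.2%; identical stream 40.9%; with same-visit components 38.8%. The overall shift is the missing share times the shift among those missing: 0.20 × (29.2 - 36.6) = -1.5, which equals 37.2 - 38.7.

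**4. How much history to keep.** A further simulation, with 80 to 100 subjects per group and about 15-30% missing, put own-history models about 0.6 to 3.3 points too low overall. Adding same-visit scores but cutting the history to the previous visit made the dropout imputations about 1 to 3.3 points too high. Full own history plus same-visit components was within about 1.1 points.

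**5. Remote visits.** With the three patient-reported scores observed and the other four components drawn independently, the composite was 3.1 to 11.3 points too low among such visits. Assumptions: same-visit correlation 0.50-0.65, within-component correlation over time 0.5-0.7, 3 or 10 earlier visits. Three earlier visits is pessimistic here: by Week 60 a complete history has 8 PA0008 visits, the Entry Visit and 4 PA0009 visits, which is 13.

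**6. Model size.** ACR is assessed at 8 PA0008 visits, the Entry Visit and 10 PA0009 visits, 19 in all. One component model has 19 + 1 Baseline + 2 covariates = 22 variables. A fully joint model has 7 × 20 + 2 = 142, against about 100 subjects per group if 200 split evenly. Adding six same-visit components to the present model gives 22 + 6 = 28.

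**The case against.** The strongest reply is that 4.2.1 adds, in parentheses, that each imputation covers all the ACR components, which could be read as joint imputation. No joint model is written, however. The listed terms contain no other component, and extending Step 1 to all seven would need 142 variables. The parenthesis says which draws are put together; it does not supply a correlation between them.

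A second reply is that SAP 8 derives response from mean imputed scores. Averaging 100 draws largely cancels the residuals, so the mechanism would hardly operate. That stands as far as it goes: the size of the effect depends on which of the two sections is programmed. It is a reason to reconcile them.

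Third, the effect is small beside sampling error. For a 50% rate the standard error is √(0.25/200) = 3.5 points overall and √(0.25/100) = 5.0 points in a group of 100. That is fair, but a shift from the imputation model is systematic and does not average out.

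Fourth, a reader might infer that this undermines the only check on NRI at Week 48, or that remote visits affect that time point. Neither is supported. SAP 8.2 reports OC beside NRI for the secondary ACR endpoints, and SAP 8.5 puts the pandemic after Week 48. The missing same-visit term itself applies at every visit in the MI table, Week 48 included.

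**Conclusion.** The concern holds for the model as written: residual same-visit correlation between ACR components is not modelled, and scores observed at remote visits after Week 48 are not used. Under assumed correlations and 10-30% missing, the reported MI rate shifts by roughly 0.5 to 4 points, downward if the draws are independent.

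It would be tempting to say that the rate is known to be biased downward, towards NRI. The documents do not support that. The size rests on assumed values. With one seed and the same dropout pattern in every component, the random streams might also align and push the rate up. That alignment is an inference about SAS behaviour and was not run in SAS. What can be said is that the dependence between components would not be estimated from the data.

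Nor does this touch the primary safety variables, the NRI results or any error rate: the study is descriptive, with no formal sample size. It is a correction worth making to one secondary-method table.

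**What to change.** For the ACR MI sensitivity analysis only:

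- Keep each component's full own history (Baseline and all visits) with region and past TNF exposure, and add the other ACR components at the same visit as predictors. Include PGADA, PtAAP and HAQ-DI observed at remote visits. Do not shorten the history to the previous visit.
- Run the components as one imputation, or use a distinct seed for each if they are run separately.
- Reconcile SAP 4.2.1 with SAP 8: derive response within each imputation and average the percentages, not from mean component scores.

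The cost is SAP wording, one more program, and a second set of imputed component values used only for this table. Each regression grows to about 28 terms. With 100 subjects in a group and 30% missing, 70 - 28 = 42 residual degrees of freedom remain; with 80 subjects, 56 - 28 = 28. That is usable but tight, so the SAP should say what happens if a regression fails, since 4.2.1 currently allows LOCF or OC instead. Protocol 13.8 names MCMC for intermittent gaps, which include remote visits. If conditional regressions replace it there, list the change in SAP 3.10. The univariate models can stay for the summaries of individual components.

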  - For CRP, the rules for handling measurements that are below the limit of quantification should be followed as per [Section 8.1.7](#). Thus, if any imputed values are  $< 0.16\text{mg/L}$ , these will be replaced with  $0.08\text{mg/L}$  prior to any subsequent reporting.
- MASES
  - For MASES, the MI model will be restricted to subjects with a MASES score  $> 0$  at PA0008 Baseline. Subjects with a MASES score of  $0$  at PA0008 Baseline will be excluded prior to performing the procedure outlined below.
- LDI
  - For LDI, the MI model will be restricted to subjects with LDI scores  $> 0$  at PA0008 Baseline. Subjects with LDI scores of  $0$  at PA0008 Baseline will be excluded prior to performing the procedure outlined below.
- DAS28[CRP]
- PsAID-9
- SF-36
  - For SF-36, this will be performed for the Physical Component Summary (PCS) score and Mental Component Summary (MCS) score only.
- HADS-A and HADS-D
  - Incidence of normal HADS-A and HADS-D scores (defined as having HADS-D  $< 8$  and HADS-A  $< 8$  at the same visit) will be derived at each visit using the values for HADS-A and HADS-D obtained after MI

The missing absolute value (not the change from Baseline) will be replaced by one of a set of plausible values, where each value is a Bayesian draw from the conditional distribution of the missing data given the observed data. The basic assumption in MI is that the underlying missing data mechanism is ignorable, eg, the missing data are missing at random.

All MI procedures will be performed using data from both PA0008 and PA0009 such that missing data across both studies will be imputed (in general, only data from PA0009 will be presented in the summary tables, with the exception of the summaries of maintenance of response where all visits in PA0008 and PA0009 will be presented). Any previous imputation

(MI or last observation carried forward [LOCF] or other imputation) performed in PA0008 will not be considered for PA0009 such that the procedure will use OC data only across both studies. Thus, the results presented in the maintenance tables for visits in PA0008 may differ from those previously reported as part of the PA0008 clinical study report.

As the PA0008 Week 48 time point is synonymous with the PA0009 EV time point, this will be incorporated once only into the model.

The SAS® PROC MI procedure will be used for the imputation.

The MI consists of 3 steps:

- The missing data are imputed  $m$  times to create  $m$  complete datasets.

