The dataset with the imputed results for each treatment arm will be combined into 1 complete dataset including each of the 100 imputations. If any imputed value is less than the lower limit of the allowable range for that parameter (as shown in Table 4-1), it will be changed to the lower limit of the range, and similarly for values higher than the allowable range. This dataset will be used to calculate the change from PA0008 Baseline variable where appropriate.

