**Table 4-1: Allowable ranges for continuous efficacy variables**

Variable	Minimum	Maximum
MASES	0	13
PASI	0	72
LDI	0	NA
DAS28(CRP)	0.988 a	NA
CRP b	0.08	NA
PsAID-9	0	10
SF-36 MCS	-3.33	80.09
SF-36 PCS	5.02	79.78
HADS-A	0	21
HADS-D	0	21
TJC	0	78
SJC	0	76
HAQ-DI	0	3
PtAAP	0	100
PhGADA	0	100
PGADA	0	100

CRP=high sensitivity C-reactive protein; DAS28(CRP)=Disease Activity Score 28 joint count C-reactive protein; HADS-A=Hospital Anxiety and Depression Scale – Anxiety; HADS-D=Hospital Anxiety and Depression Scale – Depression; HAQ-DI=Health Assessment Questionnaire - Disability Index; LDI=Leeds Dactylitis Index; LLOQ=lower limit of quantification; MASES=Maastricht Ankylosing Spondylitis Enthesitis Index; NA=not applicable; PASI=Psoriasis Area and Severity Index; PGADA=Patient’s Global Assessment of Disease Activity; PhGADA=Physician’s Global Assessment of Disease Activity; PsAID-9=Psoriatic Arthritis Impact of Disease-9; PtAAP=Patient's Assessment of Arthritis Pain; SF-36 MCS=Short Form 36-Item – Mental Component Summary; SF-36 PCS=Short Form 36-Item – Physical Component Summary; SJC=swollen joint count; TJC=tender joint count.

a For the purpose of the analysis, the actual minimum value will be set to the calculated value of  $0.36 \cdot \ln(\text{CRP}+1) + 0.96$  using the minimum CRP of 0.08mg/L.

b For the purpose of the MI any numerical CRP values obtained in PA0009 that were <0.16 mg/L will be substituted with half the lower limit of quantification (LLOQ) LLOQ from PA0008 (ie, 0.08 mg/L) prior to performing the MI. Subsequently any imputed values of <0.16mg/L will be replaced by the value of 0.08mg/L for the purpose of summaries based on imputed data. Listings will display the original result. Any CRP values of  $\geq 500$ mg/L will be

set to missing prior to performing the MI procedure; the subsequently imputed CRP value will be included in the summary tables.

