### Step 3 (Excluding CRP)

The 100 imputed datasets will be combined, and simple means and standard errors will be calculated using Rubin's rules (via SAS® PROC MIANALYZE). For calculation of other descriptive statistics (median, minimum and maximum), Rubin's rules do not apply. Multiple imputation estimates will be computed by calculating arithmetic means of the estimates from the multiple repetitions of the imputation algorithm. Thus, for median, minimum and maximum the following approach will apply:

- The data will be summarized by treatment, visit and imputation and the summary statistics will be computed.
- Results will be summarized by taking the mean value of each summary statistic at each visit across all imputations.

The number of decimal places will remain the same as the original for display purposes (ie, if the mean was presented to 1 decimal place, the mean of the means will also be presented to 1 decimal place).

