**Table 4–2: Missing data handling**

Variable	Type	Missing data handling approach		
		NRI	MI/MCMC (monotone regression)	OC
ACR20, 50, 70	Responder	P	S a	S
MASES	Continuous		P	S
LDI	Continuous		P	S
PASI75, 90, 100	Responder	P	S a	S
MDA	Responder	P		S
DAS28 (CRP)	Continuous		P	
CRP	Continuous		P	
PsAID-9	Continuous		P	
SF-36 PCS, MCS	Continuous		P	
HADS-A, HADS-D	Continuous		P	
Incidence of normal depression/anxiety status (using HADS)	Responder		P a	
TJC, SJC	Continuous		P	
HAQ-DI	Continuous		P	
PtAAP	Continuous		P	
PGADA	Continuous		P	
PhGADA	Continuous		P	

ACR=American College of Rheumatology 20, 50, 70% response criteria; CRP=high sensitivity C-reactive protein; DAS28(CRP)=Disease Activity Score 28 joint count C-reactive protein; HADS-A=Hospital Anxiety and Depression Scale – Anxiety; HADS-D=Hospital Anxiety and Depression Scale – Depression; HAQ-DI=Health Assessment Questionnaire - Disability Index; LDI=Leeds Dactylitis Index; LLOQ=lower limit of quantification; MASES=Maastricht Ankylosing Spondylitis Enthesitis Index; MCMC=Markov-Chain Monte Carlo; MDA=Minimal Disease Activity; MI=multiple imputation; NRI=nonresponder imputation; OC=observed case; P=primary method; PASI 75, 90, 100=Psoriasis Area and Severity Index 75%, 90% and 100%; PGADA=Patient’s Global Assessment of Disease Activity; PhGADA=Physician’s Global Assessment of Disease Activity; PsAID-9=Psoriatic Arthritis Impact of Disease-9; PtAAP=Patient’s Assessment of Arthritis Pain; S=secondary method;

SF-36 MCS=Short Form 36-Item – Mental Component Summary; SF-36 PCS=Short Form 36-Item – Physical Component Summary; SJC=swollen joint count; TJC=tender joint count.

a Imputation method is applied on continuous data, and response variable is derived from the continuous data based on complete dataset.

In the event that the MI model fails to converge or will not run for other reasons (eg, data issues, data distribution), alternative approaches may be considered including LOCF and /or OC summaries as appropriate. For some efficacy endpoints, these approaches may be planned already as part of the existing analyses or sensitivity analyses, and therefore it may not be necessary in all cases to provide additional summaries.

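### Clipping normal-model imputations at the scale limits biases the LDI and MASES means, and imputing CRP on the raw scale distorts its geometric mean

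*SAP*

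**What the plan says.** SAP section 4.2.1 states the scale of imputation: "The missing absolute value (not the change from Baseline) will be replaced by one of a set of plausible values". For intermittent gaps, "The imputation model based on the MCMC method will only allow multivariate normal variables as predictors". For dropout, SAP Table 4-2 and protocol section 13.8 name monotone regression. No transformation, bounded draw or predictive mean matching is specified.

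Step 2 deals with impossible values. The rule opening "If any imputed value is less than the lower limit of the allowable range for that parameter" sets the value to that limit, treats values above the range likewise, and computes change from PA0008 Baseline from the resulting dataset. Table 4-1 gives MASES a range of 0 to 13, and LDI a minimum of 0 with no maximum. Step 3 then follows: "The 100 imputed datasets will be combined, and simple means and standard errors will be calculated".

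For CRP, footnote b of Table 4-1 says: "Subsequently any imputed values of <0.16mg/L will be replaced by the value of 0.08mg/L for the purpose of summaries based on imputed data". Only afterwards, in Step 3 (CRP only), is the log taken: "The natural logarithm of the absolute values and of the ratios to Baseline will be calculated". The result is back-transformed to a geometric mean.

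Table 4-2 makes multiple imputation (MI) the primary method for MASES, LDI and CRP. Observed-case summaries are planned for MASES and LDI, but not for CRP. LOCF or observed-case alternatives may be considered "In the event that the MI model fails to converge or will not run for other reasons".

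**The concern.** Averaging after clipping is not neutral. A normal model for a score piled up near 0 puts many draws below 0, and moving them all up to 0 raises the mean. Change from PA0008 Baseline in MASES and in LDI at Week 48 are secondary efficacy variables, so a primary estimate of each is shifted. The shift grows with the amount of missing data.

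For CRP, the imputation scale and the summary scale do not match. Two errors oppose each other. Draws floored to 0.08 pull the log mean down. The remaining draws, centred on the arithmetic rather than the geometric mean, push it up. No planned observed-case table would show the net result.

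COVID-19 missingness does not reach Week 48 (SAP section 8.5). It affects later visits, where LDI and MASES cannot be assessed remotely and, per section 5.1.1, "for any missed visit or a visit conducted remotely, the CRP assessment will also be missing".

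**Working it through.** **The plan's own figure.** The only computed limit in Table 4-1 is the DAS28(CRP) minimum: 0.36 × ln(0.08 + 1) + 0.96 = 0.9877, which rounds to the stated 0.988. It reproduces. The documents give no missing rate, mean or SD for LDI, MASES or CRP, so every input below is an assumption.

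**Direction for LDI and MASES.** For a draw X ~ N(μ, σ), the mean shift from clipping at 0 is σφ(μ/σ) − μΦ(−μ/σ), which is always above 0. For MASES the loss above 13 is subtracted.
- MASES, μ = 1, σ = 1: 1 × 0.2420 − 1 × 0.1587 = +0.08 per imputed value, with 16% of draws below 0.
- MASES, μ = 1, σ = 3: 3 × 0.3774 − 1 × 0.3694 = +0.76, with 37% below 0.
- MASES, μ = 9, σ = 3: +0.001 at the bottom less 0.127 at the top = −0.13. The sign turns once the imputed mean passes mid-range, 13/2 = 6.5.
- LDI, μ = 1, σ = 5: +1.5. LDI, μ = 5, σ = 30: +9.6. With no upper limit, the LDI sign cannot turn.

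The group mean moves by the missing fraction times these amounts. Subjects with missing Baseline are excluded, so the shift passes in full to the mean change.

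**Size for LDI and MASES.** Bayesian normal-regression imputation on baseline and previous visit; missing completely at random; visit correlation 0.5; 600 replicates × 20 imputations.

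| | MASES | LDI |
|---|---|---|
| Assumed n, baseline mean | 60, about 4.6 | 40, about 50 |
| Assumed share at 0 | 45–60% | 65–80% |
| Mean change | −3.2 to −3.6 | −38 to −43 |
| Shift, 10% missing | about +0.03 (0.8–1.0%) | about +0.4 (1%) |
| Shift, 20% missing | +0.05 to +0.06 (1.7%) | about +0.8 (2%) |
| Same draws, unclipped | within 0.005 | within 0.06 |

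Monte Carlo SE was at most 0.005 for MASES and 0.07 for LDI. A separate seven-visit simulation with dropout at random agrees. At 20% dropout, the MASES change was −2.45 true, −2.44 unclipped and −2.38 clipped; the LDI change was −35.56, −35.60 and −34.91. The clipped shortfalls at 10%, 20% and 30% dropout were 0.03, 0.07 and 0.10 for MASES, and 0.4, 0.65 and 1.1 for LDI.

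**CRP, one step.** Take log-normal CRP with geometric mean G and log-SD s. The raw mean is G·exp(s²/2) and the raw SD is that mean × √(exp(s²) − 1). Draw normally with these, set values below 0.16 to 0.08, take logs and average.
- G = 3, s = 1: mean 4.95, SD 6.48. 23% of draws are floored, and the geometric mean of the imputed values is 0.71 of the truth. At 20% missing the group value is 0.71^0.2 = 0.93 of the truth.
- G = 2, s = 2: 45% are floored. The imputed geometric mean is 3.21 against 2.06 (true values floored the same way), ratio 1.56; at 20% missing, 1.56^0.2 = 1.09.

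**CRP, regression imputation.** n = 100, 20% missing, log-SD 0.9 to 1.6, 400 replicates × 15 imputations, Monte Carlo SE at most 0.004 on the log scale.

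| Assumed median (mg/L) | Geometric mean ÷ truth |
|---|---|
| 5 | 0.92–0.95 |
| 2.5 | 0.95–1.00 |
| 1 | 0.98–1.05 |
| 0.5 | 1.01–1.09 |

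Between 16% and 34% of draws were floored. At 10% missing the range was 0.96 to 1.04. Imputing log CRP gave 0.996 to 1.009 throughout. The seven-visit runs (G 1 to 10, s 0.4 to 1.5, 10% to 30% dropout) were all downward, 0.87 to 0.99. Upward shifts appear at low CRP or wide spread.

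**The case against.** The best counter-argument is that this is too small to matter. With inputs close to those above and visit correlation 0.5 to 0.85, the clipping bias was 0.06 to 0.18 of the standard error of the mean change. Higher correlation shrinks it: in that run, at correlation 0.85 and 20% missing, the MASES shift fell from 0.06 to 0.04 and the LDI shift from 1.1 to 0.65–0.75. The SAP model uses every PA0008 and PA0009 visit, so it may predict better than the simulation's. The study is single-arm with descriptive efficacy summaries, and no test depends on these means. Observed-case tables exist for MASES and LDI. The CRP table also shows the median and quartiles, and CRP is not a secondary variable. If non-responders are withdrawn, imputation under missing at random could overstate improvement, and clipping would offset that.

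Much of this stands. The size is small, it cannot be fixed from the documents, and the MASES direction is conditional. For CRP, the main cause is the raw scale with a late log; clipping alone is not to blame.

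Three parts do not answer the point. Observed-case tables expose the shift but leave the primary estimate as it is. The SAP's fallback mentions data distribution, but only as a reason the model will not run; a model that runs with many out-of-range draws does not trigger it. An accidental offset of unknown size is no substitute for a stated sensitivity analysis.

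**Conclusion.** The concern holds. The LDI direction is certain, given missing at random (the SAP's own assumption) and a regression mean that is right on average. The MASES direction also needs an imputed mean below 6.5, which is plausible this late in treatment. For CRP the direction depends on level and spread. The relative sizes are about 1% to 2% of the LDI and MASES change at 10% to 20% missing (up to about 4% at 30% dropout), and a factor of 0.92 to 1.09 on the CRP geometric mean at 20% missing. Wider assumed CRP inputs in the one-step calculation give 0.84 to 1.20. No hypothesis test or error rate is affected. It is worth correcting because the correction is cheap, but it does not threaten the study's conclusions.

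**What to change.** - **CRP:** log-transform before both the MCMC and the monotone step, back-transform, then apply the 0.08 mg/L floor. The ACR sensitivity analysis that uses imputed components should take the same CRP draws, so its results will change too.
- **LDI and MASES:** compute means, standard errors and the change from Baseline behind them from the unclipped draws of both steps. These already exist, because clipping happens only in Step 2. Apply the Table 4-1 limits only to the displayed median, minimum and maximum, and footnote this.
- Keep the observed-case summaries as the check for LDI and MASES.

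The cost is a paragraph of SAP text and a few programming options, with no new data. There are two drawbacks. Unclipped imputed values can lie outside the scale, so they should not be listed or displayed. The mean and the median in one table would also come from differently treated draws.
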